A standardized post-operative regimen will be used, consisting of a single belladonna & opium suppository, a single dose of ketorolac 30mg IV, and ondansetron 4mg IV. A single dose of hydrocodone 5mg with acetaminophen 325mg PO will be available PRN pain.

To qualify for discharge from the PACU, all patients will have had to have met a standardized set of discharge criteria. They will have to have ambulated, voided, tolerated PO intake, and have pain subjectively adequately controlled.

On PACU discharge, patients will be given a prescription for 20 tablets of 50mg diclofenac, 20 tablets of acetaminophen 650mg to be taken on a scheduled basis every 6 hours, and mirabegron 50mg once daily PO to be taken until stent removal [15]. There is no universal standard of care discharge regimen after ureteroscopy, but a similar one to this has been shown to be safe and effective [26]. Patients will receive a standardized sheet of return precautions. They will receive packets of questionnaires to be completed along with pre-addressed and pre-stamped envelopes. They will be instructed to only seek pain medication from the urology team for the next month. Should they have need for further pain medication, patients will be instructed to call the clinic [see supplementary material]. They will be offered their choice of another 3 days of NSAID or oxycodone 5mg q6h PRN pain 6 tablets. Further treatment will be at provider discretion. The clinic staff will be instructed to record these prescriptions.

THERAPEUTIC AND DIAGNOSTIC AGENTS

Pregabalin is an oral agent approved for use in fibromyalgia and neuropathic pain. A single dose of 300mg PO will be given to all patients.

RECRUITMENT PLAN

Patients will be recruited from the practice of [name] in the Division of Urology, Department of Surgery. The study will be introduced to every eligible patient scheduled for ureteroscopy with stent placement by the participating consenting physicians from the Department of Surgery-Urology Division and a written consent obtained prior to surgery by the consenting research personnel. Candidate subjects will be provided time to consider the study, to read the informed consent document at their convenience, and discuss the study with family and others, as desired. It will be clearly indicated that non-enrollment in the study will not negatively affect the patient's care.

PRETREATMENT EVALUATION

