
- Yes
- No

On what side was ureteroscopy performed?

- Right
- Left
- Bilateral
- None

Was the patient extubated in the OR?

- Yes
- No

What was the planned disposition for the patient?

[figure not shown]
- Home from PACU
- Floor
- ICU

Pacu Discharge

At one hour post op: How much pain is the patient in?

No pain

Most pain

(Place a mark on the scale above)

Where is the patient going after PACU discharge?

- Home from PACU
- Floor
- ICU

How long was it (in minutes) from when the patient arrived in the PACU until they went home?

Please indicate if the patient experienced any of the following since surgery. A check indicates that the patient did experience this adverse event.

	Yes
Dizziness	
Vertigo	
Incoordination	
Balance disorder	
Ataxia	
Diplopia	
Blurred vision	
Amblyopia	
Tremor	
Somnolence	
Confusional state	
Disturbance of attention	
Thinking abnormality	
Euphoria	
Edema	
Peripheral edema	
Asthenia	
Fatigue	
Dry mouth	
Constipation	
Amnesia	
Back pain	
Contusion	
Depersonalization	
Diarrhea	
Fall	
Headache	
Hyperhidrosis	
Increased appetite	
Infection	
Memory impairment	
Nausea	
Nervousness	
Neuropathy	
Pain	
Paresthesia	
Sinusitis	

Upper RTI

Vomiting

What are the patient's expectations regarding post-operative pain?

- There will be minimal pain regardless of treatment
- The pain regimen being given for discharge will be sufficient
- More pain medication will be required

What pain control does the patient believe they will need in addition?

- Opioid pain medication
- Non-opioid pain medication only

Aldrete

Time to Aldrete 9 or 10:

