(Number of minutes from arrival in PACU to modified Aldrete score of 9 or 10. In 15 minute increments)

Early patient questionnaire

Date form was filled out:

How satisfied are you with your urology team?

- very dissatisfied dissatisfied
 satisfied very satisfied

How satisfied are you with your pain control as related to your urologic procedure?

- very dissatisfied dissatisfied
 satisfied very satisfied

Do you still have a stent in place?

- No
 Yes - the one from your initial surgery on [surg_date]
 Yes - the stent is from a different procedure

How satisfied are you with your stent related symptoms?

- very dissatisfied dissatisfied
 satisfied very satisfied

Please tell us the pain medications you have taken since surgery. For each, please list the name of the medication, the dosage, and the total number. Use a new line for each new medication.

Evaluation of trial

Please complete the survey below.

Thank you!

84) Date: _____

85) Evaluator is: Patient
 Treatment Doctor
 Treatment Nurse
 Study Staff

86) What could be done to make the study better? Was there anything important to you that was not evaluated? _____

Evaluation of trial PACU nurse

Date:

What could be done to make the study better? Was there anything important to you that was not evaluated?

30 Days Post Op Study

How many pills of oxycodone 5mg did the patient have prescribed?

What other narcotics was this patient prescribed? Please include the name of the narcotic along with dosage and number of pills.

How many total ED visits or hospitalizations did the patient have?

How many ED visits or hospitalizations did the patient have related to their ureteroscopy?

How many contacts with the urology team did the patient have?

For how many days was the stent in place? Indicate 31 for stent still in place at 30 days post-op.

Unanticipated Contact

Date of unanticipated contact:

What kind of unanticipated contact did you have with the patient?

- Phone
- Email or chart message
- Regularly scheduled clinic appointment
- In clinic but not at a regularly scheduled appointment
- In the emergency department
- As an inpatient
- Other

What was the unanticipated contact?

Was this related to stent discomfort?

- Yes
- No

Was pain medication prescribed?

- Yes - an NSAID was prescribed
- Yes - the study opioid was prescribed
- Yes - another opioid was prescribed
- Yes - another pain medication was prescribed
- No

What was the other pain medication prescribed?

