The patient's disposition will be:

- Home - they do not need to be evaluated
- Clinic - they will be in clinic in the next 3 business days for evaluation
- Emergency department - they require evaluation in the emergency department
- Hospital - they will be directly admitted
- Other

What is the patient's disposition?

Does this constitute something that should be brought to the attention of the study physicians?
In addition to submitting this form, you must email the study physicians

- Yes
 - No
- (Examples would include: serious adverse event related to study medication, serious change in health status, serious patient concern)

Late patient questionnaire

Date form was filled out:

Do you regularly take narcotic pain medication?

- Yes
- No

Have you had any issues related to your procedure on [surg-date] that has not yet been recorded?

- Yes
- No

Please describe the issue:

USSQ

Date completed:

Urinary index score:

Pain index score:

General health index score:

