STATISTICAL ANALYSIS PLAN

Project Title: Perioperative pregabalin as part of a multimodal treatment plan for pain after

ureteroscopy with stent placement: a pilot

IRB Number: 2013680 Version Number: 1.1 Version Date: 11/20/2019

Principal Investigator: [name]

Funding Source: Departmental Clinical Trial Phase: Not Phased

Clinicaltrials.gov Number: NCT03927781 Study Drug/Study Device: Pregabalin

Principal Investigator	[name]	Department of Surgery Urology
		Division
Co-Investigator	[name]	Department of Surgery Urology Division
Consenting Professional(s)	Donartment of Surgery	DIVISION
Consenting Professional(s)	Department of Surgery-	
Department	Urology	

University of Missouri University Hospital Department of Surgery Urology Division [name] Descriptive statistics (counts, proportions, medians) will be used to describe all data. We will describe the demographic information of the patients enrolled and the number of patients approached to meet full enrollment. We will assess the proportion who anticipated needing opioid pain medication, who appropriately received pregabalin, who received opioid pain medication at discharge, who had emergency room visits or hospitalizations in the first 30 post-operative days, and who received opioid prescriptions within the first 30 post-operative days. We will describe the number of oral morphine equivalents prescribed. We will include median USSQ scores. We will describe proportions reporting possible adverse effects and pain level reported. All analyses will be performed in R version 3.5.1. There will be no statistical tests performed.

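### The PACU adverse event checklist cannot separate a patient with no events from a list that was passed over, and neither document says how a blank is counted

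*Protocol*

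**What the plan says.** **Checklist.** The Pacu Discharge form (Protocol, Appendix 1) asks about events since surgery in a list of 39 items with one column, headed *Yes*. The instruction is: "A check indicates that the patient did experience this adverse event". There is no *No* column, no none box and no code for not assessed. The same form also asks for a pain mark, the patient's destination, the time in PACU ("How long was it (in minutes) from when the patient arrived in the PACU until they went home") and expectations about pain. The evaluation schedule gives the respondent as the patient or the PACU nurse.

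**Endpoints and analysis.** Drug-related adverse events and correct use of the study instruments are both primary endpoints in the Protocol. The SAP states: "We will describe proportions reporting possible adverse effects and pain level reported". Neither document gives a denominator or says how an unticked list is treated. Under Quality Assurance, the Protocol promises periodic reports on missing and inconsistent data, in general terms.

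**Opioid use.** The Early patient questionnaire, due at days 3 and 7, opens with "Date form was filled out". Later it has a free-text item on all pain medications: "Please tell us the pain medications you have taken since surgery". It has no separate yes/no question on opioids. Two other instruments can record a negative: the 30-day staff form asks for a count ("How many pills of oxycodone 5mg did the patient have prescribed"), and the Late patient questionnaire has a Yes/No item ("Do you regularly take narcotic pain medication").

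**The concern.** A tick-only list gives an empty set of boxes two meanings: the events were asked about and did not occur, or nobody went through the list. Nothing on the form shows which, and the task is shared between patient and nurse. The ambiguity falls on the pilot's main safety measure. If blanks are taken as negatives, any error lowers the adverse event proportion and makes the drug look better tolerated.

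The second primary question is touched as well. The pilot is meant to find out whether its instruments are used correctly, and a list passed over inside a returned form is a misuse that this form cannot reveal. The general data quality reports do not help, because a blank that is also a valid answer is not flagged as missing.

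The early medication item has a milder form of the same problem. An empty text box leaves opioid use at days 3 and 7 open, and two of the Protocol's secondary endpoints (how many patients take narcotics, and the morphine equivalents they use) depend on it at those times.

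**Working it through.** **Is there another structured record of side effects?** The Protocol's Toxicities/Side Effects section names a PACU side effect questionnaire and a PACU nursing questionnaire. The nurse-completed instruments in Appendix 1, apart from the shared PACU form, are the Aldrete score and the nurse's evaluation of the trial. The first records recovery and the second asks how to improve the study; neither asks about side effects. The Early questionnaire has no adverse event item, and the Late questionnaire's general question on issues starts at day 30. The checklist is therefore the only structured side-effect list shown.

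**What can and cannot be detected.**
- Whole form missing: the pain mark, destination, minutes and expectations are all empty, so it is detectable.
- Form completed, list passed over: those fields are filled and no box is ticked. A patient with no events gives the same record.

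**Inputs for the size.** n = 10 completing patients (Protocol, Sample Size). The true proportion p and the number m of lists passed over are assumptions; the documents give neither. The plan's only design figure, 20 enrolled for 10 completers, does not bear on this point, and there is no stated adverse event rate to reproduce.

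**Formula.** If the list is passed over regardless of whether events occurred, and blanks count as no:

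expected reported proportion = p × (n − m)/n

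For n = 10:

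| m | p = 20% | p = 30% | p = 50% |
|---|---|---|---|
| 0 | 20% | 30% | 50% |
| 1 | 18% | 27% | 45% |
| 2 | 16% | 24% | 40% |
| 3 | 14% | 21% | 35% |
| 5 | 10% | 15% | 25% |

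For example, 50% × (10 − 2)/10 = 40%. Each list passed over removes a tenth of the true value. If all 20 enrolled patients were the denominator, two such lists would give 50% × 18/20 = 45%.

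**No events seen.** The exact two-sided 95% upper limit for 0 of n is 1 − 0.025^(1/n). For 0 of 10 it is 30.8%. If two of those ten lists were never gone through, the evidence is 0 of 8 and the limit is 36.9%. The SAP plans no intervals; these only show how much information is lost.

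**With the number not assessed recorded.** Using answered lists as the denominator gives an expected value of p, under the same assumption. If that assumption is doubted, bounds can be reported: count all blanks as no, p(n − m)/n, or all as yes, [p(n − m) + m]/n. With an answered proportion of 50%, n = 10 and m = 2, these are 40% and (4 + 2)/10 = 60%. Neither step is possible while m is unknown.

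**The case against.** The strongest reply is that the documents never say a blank is scored as no. That is correct: they are silent, and the downward bias is conditional on that scoring. Silence is still a gap, because an unticked box has to be counted somehow and the form gives the analyst nothing to decide with.

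A reader might infer that skipped forms go unseen. They do not; a form that was never done is empty throughout. There is also a partial check inside the form: *Pain* is one of the 39 items, so a blank list beside a clearly non-zero pain mark would look inconsistent. That helps only for patients with pain, and no document plans the comparison.

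A reader might also infer that the medication item cannot record an absence of opioids. It can. A patient may write that nothing was taken, or list non-opioids only. Since every patient is prescribed "20 tablets of acetaminophen 650mg to be taken on a scheduled basis every 6 hours", most would have something to list, and a wholly empty box would stand out. The day 7 answer also covers the period since surgery, though it does not restore the day 3 time point. Nor are the SAP's opioid results exposed: they concern receipt at discharge, prescriptions within 30 days and morphine equivalents prescribed, none of which uses this text box.

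The Protocol has other safety routes: graded complications, serious adverse event reporting, the unanticipated contact form and the late questionnaire. These give some cover for serious or later events. None of them is a structured list of the transient cognitive and coordination effects that the Protocol itself names as the drug's principal side effects.

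Finally, the printed appendix may not show which fields are set as required. On a tick-only list such a setting would not settle the matter, because a patient with no events has no box to tick.

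**Conclusion.** The point holds for the checklist. A list passed over within an otherwise completed PACU form cannot be told apart from a patient with no events; this affects a primary safety endpoint and is invisible to the endpoint on instrument use. If such blanks count as no, the adverse event proportion shrinks by (n − m)/n: by a fifth with two of ten lists passed over. That figure rests on an assumed m and on omission being unrelated to events. The size of any bias cannot be fixed from the documents, nor do they show that any will occur.

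For opioids the point is smaller: an empty medication answer is ambiguous for the Protocol's early narcotic-use and morphine-equivalents-used endpoints only. The documents do not support the wider readings that skipped forms are scored as negative, that missed forms are hidden, or that the SAP's prescription-based opioid results are biased.

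In a descriptive ten-patient pilot this is a modest matter, worth correcting because the correction is nearly free and the instruments are meant to inform a later trial.

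**What to change.** - **PACU checklist:** add required responses for none of these and for not assessed. A required field stating whether all items were asked (yes/no) would serve equally.
- **Day 3 and day 7 questionnaire:** before the free-text item, add a yes/no question on whether any opioid has been taken since surgery.
- **SAP:** state that each proportion uses as its denominator the patients who answered that section, and that the number not assessed is reported beside it.

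The cost is an edit to the REDCap and paper forms, one SAP sentence and a few seconds per form.

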Appendix 2 – USSQ

We are unable to include this due to copyright.

Appendix 3 – Aldrete

PACU Discharge form

Subject ID: _____

Baseline BP: ____ / ____

Date: ____ / ____ / ____

Record the first Aldrete score at 15 min and take off O2 mask

Aldrete	15 min	30 min	45 min	60 min	75 min	90 min	115 min	120 min	Comments
Respiration									
O2 Saturation									
Consciousness									
Circulation									
Activity									
Total									

Time when Aldrete score is 9 or 10: ____ : ____ (record time or call anesthesia attending)

Chart 1. The 'modified' Aldrete Scale			
RESPIRATION	2	1	0
	Able to take deep breath and cough	Dyspnea/Shallow Breathing	Apnea
O2 SATURATION	2	1	0
	Maintains > 92% on room air	Needs O2 inhalation to maintain O2 saturation > 90%	Saturation < 90% even with supplemental O2
CONSCIOUSNESS	2	1	0
	Fully awake	Arousable on calling	Not responding
CIRCULATION	2	1	0
	BP ± 20mmHg pre op	BP ± 20-50mmHg pre op	BP ± 50mmHg pre op
ACTIVITY	2	1	0
	Able to move 4 extremities voluntarily or on command	Able to move 2 extremities voluntarily or on command	Able to move 0 extremities voluntarily or on command

Appendix 4 – Post-op study specific instruction

Post-Operative Supplementary Instructions

Thank you very much for participating in our study. Please see your other discharge forms for details of when to return to regular activity and when you need to contact a provider urgently.

An important part of this study is to keep track of how you are doing. We will also be keeping track of any pain medicine you require.

You should get a packet of questionnaires to leave with. Please complete these on the dates indicated. For some forms, we will either email you (if you provided authorization) or call you to ensure that you have done the questionnaire.

You are being discharged with a pain regimen that we anticipate will be able to control your pain. If you need other pain medication, we ask that for the **first 30 days after your procedure you only get this from the study team.**

To do this, please contact us as follows:

During regular business hours, please call **[contact]**

After hours or if unable to reach anyone at the above number, please call **[contact]** and ask for the **urology resident on call**

If you have feedback on the study at any time, please contact us

If you have any major medical changes, please contact us

If you have any issues related to your procedure or participation in this study, please contact us

Appendix 6 – HIPAA waiver of authorization

**UNIVERSITY OF MISSOURI – COLUMBIA
INSTITUTIONAL REVIEW BOARD**

Waiver or Alteration of Health Information Portability and Accountability Act (HIPAA) Authorization for the Use and/or Disclosure of Protected Health Information (PHI) Resulting from Participation in a Research Study

PRINCIPAL INVESTIGATOR NAME: [name]

IRB PROJECT #: 2013680

PROJECT TITLE: Perioperative pregabalin as part of a multimodal, opioid-sparing treatment plan for ureteral stent symptoms after ureteroscopy: a pilot

Please check whether you are requesting a HIPAA waiver or alteration:

- Waiver
 Alteration

If you selected alteration, indicate what is being altered:

Why do you need this waiver or alteration? Select all that apply:

- Pre-Screening** of health care records to identify potential subjects for the research.
 Retrospective review of records that exist at this time, to obtain information without the subject's written authorization.
 Prospective review of records to obtain information that is still being collected or that will be collected in the future, without the subject's written authorization.

Justification for a Waiver or Alteration:

To obtain approval for a waiver or alteration of Health Information Portability and Accountability Act (HIPAA) authorization for the use and/or disclosure of Protected Health Information (PHI) resulting from participation in a research study, the project must meet the criteria listed below. Please explain how your study meets these criteria.

1. Check the identifiers to be collected:

- | | |
|--|---|
|  Name |  Address |
|  Elements of Dates related to an individual |  Telephone numbers |
|  Fax Number |  Email Address |
|  Social Security Number |  Medical Record Number |
|  Health plan beneficiary number |  Account numbers |
|  Certificate or license numbers |  Any vehicle or other device serial number |
|  Web URL |  Internet Protocol (IP) Address numbers |
|  Biometric identifiers (finger or voice print) |  Photographic image – (Not limited to images of the face) |
|  Any other characteristic that could uniquely identify the individual | |

2. Check the type of information to be collected:

- | | |
|--|--|
|  Radiology Images |  Discharge Summaries |
|  Radiology Imaging Reports |  Health Care Billing or Financial Records |
|  EKG |  Consultations |
|  Progress notes |  Medications |
|  History and Physical exams |  Emergency Medicine reports |
|  Operative Reports |  Dental Records |
|  Pathology Reports |  Demographic information such as age, race, etc. |
|  Laboratory Reports |  Questionnaires, Surveys and/or Subject Diaries |
|  Photographs and or Videotapes |  Audiotapes |
|  Social Security Number (This is only collected for billing purposes and not shared with the sponsor) | |
|  Other (List Here): _____ | |

3. List the source(s) of the PHI.

- Paper record in clinical areas
- Electronic Medical Record (EMR)
- Data being extracted from an MU databank
- Electronic databases in ancillary units (lab/pathology, radiology, pharmacy, etc.)
- Other – Describe: _____

4. Provide a brief explanation of why the research activity to be permitted by this waiver or alteration involves no more than minimal risk to the subjects.

The minimum amount of information required for research purposes will be used. Only collection of this information will be covered by the waiver. This portion of the study represents a retrospective examination of information gathered for clinical purposes. There is no chance of physical harm or discomfort to the subject.

5. Explain why this waiver or alteration will not adversely affect the privacy rights and welfare of the subjects.

All data will maintained according to university policy. This will be in a secure online or physical repository. Only the necessary staff will have research to the data. If used, the data will be reported without any identifiers. This use of data is very unlikely to result in harm, insult, injury to relationship, loss of job or insurance, or well being of the patient.

6. Demonstrate the research involves no more than minimal risk to the privacy of subjects by describing the plans requested below:

a. Describe the plan to protect the identifiers from improper use and disclosure.

No identifiable data will be reported.

b. Indicate where the PHI will be stored.

PHI will be stored according to university policy in an online secure repository or in a physically secure location.

c. Indicate who will have access to this information.

Only research staff who require access to this information will have it.

d. Describe the plan to destroy the identifiers at the earliest opportunity consistent with the conduct of the research. Include how and when identifiers will be destroyed. If there is a health or research justification for retaining the identifiers or such retention is otherwise required by law, provide the reason to retain identifiers.

In accordance with recordkeeping requirements for the pilot study, identifiers must be retained.

Timeline to Destroy:

- End of Study
- Months or years after end of study – Specify #: 7 years
- Other – Specify: _____

7. Explain how your research meets both of the following criteria for a waiver or alteration:

a. The research could not practicably be conducted without the waiver or alteration [indicate why it is very difficult to obtain authorization from the participants (inconvenience, time, resources are not acceptable criteria)].

This is for pre-screening to find patients for a larger study. It is not possible to have all patients consent to this.

b. The research could not practicably be conducted without access to and use of PHI.

This is for pre-screening which requires access to PHI.

